Recruitment was conducted between the dates of the 1st of October and the 2nd of November, 2020. Participants in the intervention group commenced the education and hypnotic intervention on November 2nd, 2020. Participants were recruited directly online using the Pelvic Pain Foundation of Australia social media sites, and via health practitioners working with PPP, who provided study information to their clients. Participants who expressed an interest were contacted by email, and provided with the Participant Information Sheet and Consent Form. Once consent forms were received, participants were sent the questionnaires for the outcome measures.

Allocation

Participants were allocated to either the intervention or waitlist control groups. The intervention group received seven weeks of hypnotic intervention therapy in the form of audio recordings of hypnosis sessions provided online. The waitlist control group received no intervention.

Blinding

Blinding for participant or psychologist was not possible, as participants required notification of the time line for hypnotic intervention. A total number of 40 participants commenced the trial, with 20 allocated to the intervention group, and 20 allocated to a waitlist control. Participant details were placed into unlabelled, sealed, envelopes.

Randomization

Randomization was conducted using a basic randomization software template. Once group allocation was complete, participants were notified of their group

allocation. The waitlist control group received support for two months upon completion of the trial. Recruitment and contact with participants were undertaken by the primary researcher, whereas randomization was undertaken by an independent statistician.

Procedure

After allocation, participants in the intervention group were sent a link to provide them with access to the hypnosis recordings when the trial commenced. The information sheet and seven hypnosis recordings were accessible on a website for the study. The intervention also contained one session of education regarding PPP and hypnosis. Participants in the intervention group were instructed to read the health resources provided, that included information on the anatomy of the pelvis and the basics of pain education before commencing the hypnosis recordings. Intervention group participants then completed seven online hypnosis recordings, one per week for seven weeks.

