The intervention group were also instructed to continuing listening to recordings from the weeks prior whilst progressing through the intervention to week seven. The intervention group participants were contacted by phone or email once weekly during the trial, to discuss their progress and to seek feedback on their experience with the intervention. Following the conclusion of the intervention at week seven, participants completed the outcome scales assessed at the beginning of the study, and provided feedback on the study overall. The control group completed the concluding outcome measures at the same time. This occurred across the week of the 21st of December, 2020.

The waitlist control were given access to the study materials including information on the anatomy of the pelvis and the basics of pain education, as well as the hypnosis sessions for two months after the study concluded. This was so that they could also have the benefits of the intervention, without interfering with the results. No changes to the study methodology were made once the pilot RCT commenced.

Education

Participants in the intervention group received education about the pelvis, pelvic muscles, pelvic pain and hypnosis prior to commencing the hypnotic intervention.^{10-11,12-14} This included information on pain and the brain, how to become familiar with the pelvic muscles, and how to tense and relax the pelvic muscles. The education components were heavily based on the 'explain pain' resources for chronic pain management by Moseley and Butler³¹ and consultation with two experienced physiotherapists.

Hypnosis script development

A series of seven hypnosis scripts were developed. This number was based on the number of scripts used in other evidence-based hypnosis protocols for IBS and chronic pain.^{26,32} These scripts were developed based on resources on script structure provided by Mason³³ and Yapko.³² Induction is the process of preparing the person to go into a state where they are focused and more open to suggestion, called a 'trance' state. After promoting relaxation, every hypnosis script starts with an induction.³² The inductions chosen for the script development in this study were based on a selection commonly used for hypnosis in general, as well as those used regularly with reference to chronic

pain and IBS. The following sources were consulted with reference to the development of the inductions used for the scripts in this study.³²⁻³³

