This study utilized a series of questionnaires at baseline and the conclusion of the pilot trial in line with the outcomes of interest. The outcome measures included the Generalised Anxiety Disorder Scale 7-item (GAD-7)³⁴, Patient-Health Questionnaire 9-item (PHQ-9)³⁵, 10-point Visual Analogue Scale measuring pain severity, Brief-COPE³⁶, Pain Catastrophizing Scale (PCS)³⁷, the Pain Disability Index (PDI)³⁸ and the Short Suggestibility Scale (SSS)³⁹. The questionnaires were converted to an online format using SurveyMonkey⁴⁰ software, then a link to the study website was emailed to participants. The questionnaires utilized are listed below.

Feedback on recording use and the study

The primary outcome was to establish the feasibility of the trial. Therefore, the intervention group was asked to provide weekly feedback on the recordings and study overall and at the end of the pilot trial. At baseline, we asked participants to give an overview of their experience with chronic pelvic pain in an open response dialogue box. Each week of the seven week trial, participants in the intervention group were asked how many times they listened to each recording and for their feedback. We also asked for feedback on the trial overall in an open dialogue box in the concluding measures.

Questionnaires for the outcome variables

Our primary outcomes of interest were anxiety and depression. The secondary outcomes of interest included perceived pain severity, life impact of pain, coping styles and pain catastrophizing. We identified our outcomes of interest from previous research on chronic pain, previous systematic reviews and a recent scoping review looking at predictors of mental health outcomes for women with CPP.¹¹⁻¹⁴

Generalised Anxiety

Generalised Anxiety was measured using the GAD-7³⁴ at baseline and trial conclusion. The GAD-7³⁴ is a 7-item self-administered scale with seven questions related to Generalised Anxiety Disorder symptoms according to the Diagnostic and Statistical Manual 5th Edition (DSM-V).⁴¹ Persons completing the GAD-7³⁴ are asked '*over the last two weeks, how often have you been bothered by the following problems*', before being presented with the seven questions about anxiety symptoms, such as '*feeling nervous, anxious or on edge*'. Each of the seven items has a four-point Likert response scale, with

responses ranging from 0 (not at all) to 3 (every day). Total scores range from 0 to 21, with a higher score representing greater anxiety.

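### Adverse events, transient worsening and treatment changes elsewhere are not systematically asked about in either arm, and the only interim channel described is in the intervention arm

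*Combined protocol and SAP*

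**What the plan says.** The Procedure section gives the intervention arm a personal contact every week: "The intervention group participants were contacted by phone or email once weekly during the trial, to discuss their progress". The section on feedback under Outcome measures adds the content: "participants in the intervention group were asked how many times they listened to each recording and for their feedback". Both passages name the intervention arm.

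For the comparator, the Allocation section says: "The waitlist control group received no intervention". Support is placed afterwards, in the Randomization section: "The waitlist control group received support for two months upon completion of the trial". No contact with these women between baseline and close is described.

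Scales are given twice: "This study utilized a series of questionnaires at baseline and the conclusion of the pilot trial". Both arms complete them together at the end: "The control group completed the concluding outcome measures at the same time". The feedback section also mentions a free-text box in the closing measures, without saying clearly whether waitlist women received it. The Statistical analyses section compares change between arms with a linear mixed model and a group-by-time term. The document contains no definition of an adverse event, no harm question, no item on treatment elsewhere and no analysis of harms.

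**The concern.** A pilot with feasibility as its first purpose should show whether women tolerate the recordings and whether anything else changed in their care meanwhile. Here such information enters the data mid-trial only if a woman volunteers it, and only one arm has a described occasion to do so.

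Three consequences follow. Volunteered events would come mainly from the treated arm even if the true rates were equal. If nothing is volunteered, a reader may take silence for safety, although nobody was asked. And treatment begun elsewhere, which is plausible among women told to wait, cannot be considered when the group-by-time result is interpreted. A main trial planned from this pilot would inherit all three gaps.

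**Working it through.** The plan gives no figure on harms to reproduce. The only sample-size figure, a cited minimum of 10 per arm, does not bear on this point.

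**Contacts.** Inputs: 20 women per arm (Blinding section) and one contact a week for seven weeks (Procedure). Intervention arm: 20 × 7 = 140. Waitlist arm: none described.

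**What the closing scales look back on.** The intervention began on 2 November 2020 (Recruitment), and closing measures were taken in the week of 21 December (Procedure), which is 49 days from the start. The GAD-7 and PHQ-9 ask about the last two weeks.
- Form completed on 21 December: recall reaches back to 7 December, so 49 − 14 = 35 of the 49 days are uncovered (71%, weeks 1 to 5).
- Form completed on 27 December: recall reaches back to 13 December, so 41 of the 49 days are uncovered (84%).
- The pain item asks for current pain only. The document gives no recall period for the PCS or PDI.

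Recordings were introduced one a week, so the first five were introduced before the earliest window opens. Women were told to keep using earlier recordings, so a recurring reaction could still show on the scales. One that resolved would not.

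**What each arm can report.**

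| Event | Intervention arm | Waitlist arm |
|---|---|---|
| Worsening of mood, pain or function present at close | Scales, compared by group-by-time | The same |
| Worsening that resolved before close or before the recall window | Only if volunteered | No interim route described; closing text box if received |
| Distress from a recording | Only if volunteered | Not applicable |
| Stopping because of a recording | Listening count shows the stop, not the reason | Not applicable |
| Treatment changed elsewhere | Only if volunteered | No interim route described; closing text box if received |

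**Effect on a comparison of volunteered events.** Let the true proportion with an event be p in both arms and the proportion of events that reach the data be c. Expected reports are 20 × p × c, so the ratio between arms is c(intervention) / c(waitlist), whatever p is. The document gives neither p nor c; the following values are assumptions.
- p = 10%, c = 90% and 30%: 20 × 0.10 × 0.90 = 1.8 against 20 × 0.10 × 0.30 = 0.6, a threefold apparent excess with no true difference. The chance of at least one report is 1 − 0.91^20 = 84.8% against 1 − 0.97^20 = 45.6%.
- p from 5% to 30%, same capture: 0.9 to 5.4 against 0.3 to 1.8, again threefold.
- c = 90% in both arms: equal counts, and the distortion disappears.

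**What zero events would show.** Even if all 20 women in an arm were asked and none reported an event, the exact two-sided 95% upper limit is 1 − 0.025^(1/20) = 16.8%. If they were not asked, no limit can be stated.

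**The case against.** A reader might infer that any worsening can come only from treated women and can never be compared. The document does not support that. Both arms complete the same scales at the same closing time, higher scores are worse on the GAD-7, PHQ-9, pain, PCS and PDI, and the model compares change by arm. Worsening that persists to week seven is collected and compared.

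Nor does the document say that waitlist women had no contact; that is inferred from silence. They may also have had the closing text box, so it would be wrong to assume that nothing could be recorded from them. A reader might also suspect particular recordings of causing harm because of their content, but Table 1 links none of them to distress.

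The remaining objections are that weekly feedback serves feasibility and waitlist women had no recordings to comment on; that a little-contacted waitlist is a legitimate choice; that no harm count or safety conclusion is planned, so no planned analysis is biased; and that 20 women per arm cannot give a precise harm rate.

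All of this stands as a limit on the point. It does not remove it. The scales give mean change, with no analysis of individual deterioration described. They do not cover most of the seven weeks, the reason for stopping, or care received elsewhere. Low precision is a reason for modest claims, not for leaving the question unasked.

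**Conclusion.** The point holds as a gap in data collection that is worth closing. It is not a flaw in the efficacy analysis. Adverse events, worsening that resolved before close, and co-interventions are not systematically asked about in either arm. The only interim channel described is the weekly contact in the intervention arm: 140 contacts, against none described in the other arm. On the two scales with a stated recall period, 35 to 41 of the 49 days fall outside the window.

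The day counts rest on the stated start date and closing week. The waitlist figure rests on the document describing no contact. The threefold ratio depends entirely on assumed capture rates of 90% and 30%; it shows the direction of the distortion and does not estimate it. Two conclusions need no assumed rate: events volunteered in the weekly contacts are not a fair between-arm comparison, and an absence of reports would not be evidence of safety.

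**What to change.** Add closed items to the closing online form, worded identically in both arms and covering the whole seven weeks:
- any new or worse pain or mood symptom (yes/no, severity, whether care was sought);
- any treatment started, stopped or changed.

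For the intervention arm only, add whether a recording caused distress, which one, and whether she stopped because of it. Compare arms only on the shared closed items. List events volunteered in the weekly contacts separately, without an arm comparison. State whether waitlist women receive the closing text box.

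The cost is a few items in a survey tool already in use, for 40 women, with no extra staff or visits. Asking once at the end leaves some recall loss. An optional identical mid-trial form would reduce it, at the price of slightly more attention to the waitlist arm, which could slightly shrink the observed difference.

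If collection is already complete, state in the report that harms and co-interventions were not systematically collected, draw no safety conclusion, and carry the items into the main trial.

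### The use and acceptability data behind the feasibility outcome are self-reported, with weekly feedback sought by the primary researcher by phone or email; they may be misreported and the plan has no check.

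*Combined protocol and SAP*

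**What the plan says.** All references are to the combined protocol and SAP.

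- **Outcome and its data (Feedback on recording use and the study).** "The primary outcome was to establish the feasibility of the trial". The next sentence opens with 'Therefore' and gives this as the reason for asking the intervention arm for feedback weekly and at the end. In each of the seven weeks, "participants in the intervention group were asked how many times they listened to each recording and for their feedback". The mode of collecting the counts is not given.
- **Weekly contact (Procedure).** Intervention participants were "contacted by phone or email once weekly during the trial, to discuss their progress and to seek feedback on their experience".
- **Who makes contact (Randomization).** "Recruitment and contact with participants were undertaken by the primary researcher". An independent statistician did the randomization; no independent person is named for collecting feedback.
- **Where the recordings are (Procedure).** "The information sheet and seven hypnosis recordings were accessible on a website for the study". Participants received a link. Access logs, play counts, individual links and staged release are not mentioned.
- **End-of-trial feedback (Feedback on recording use and the study).** "We also asked for feedback on the trial overall in an open dialogue box in the concluding measures".
- **Survey platform (Outcome measures).** "The questionnaires were converted to an online format using SurveyMonkey". Whether responses were anonymous or coded is not stated.

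**The concern.** A feasibility pilot of a self-directed audio programme needs to know whether people played the recordings and what they thought of them. Here both answers come from the participant. At least the weekly feedback goes, in identifiable form, to the person who recruited her. She has been told to complete one new recording a week and to keep replaying earlier ones, and is then asked how she got on. That setting favours generous answers about use and mild answers about quality. Phone and email are both allowed, so the setting may also differ between participants.

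Recall adds a second source of error. The question is how often each recording was played, and the list of recordings in use grows week by week.

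At stake is the interpretation of the outcome the plan calls primary. If use was partial but reported as near complete, the pilot would describe the programme as better used than it was, and a main trial could be planned on too high an adherence figure. A null result on the questionnaires would also be harder to read without knowing the true exposure.

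**Working it through.** **1. Is there a figure to reproduce?** No. The plan states no uptake rate, adherence threshold, acceptability target or progression criterion. The only sizing figure, a minimum of 10 per arm in Sample size justification, does not bear on this point.

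**2. What is documented and what is inferred.**

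| Element | Status |
|---|---|
| Listening counts are self-reported | Stated |
| Weekly feedback is sought by phone or email | Stated |
| The primary researcher handles participant contact | Stated |
| These data serve the feasibility outcome | Stated |
| Counts were taken in the phone or email contact | Inferred: same arm, same weekly timing, and the only weekly channel described |
| End-of-trial feedback came through researcher contact | Contradicted: it was free text within the concluding measures |
| An objective usage record exists | Not mentioned |

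**3. Burden of recall.** Assume that each week's question covers every recording released so far. Each person then gives 1 + 2 + ... + 7 = 28 counts. With 20 in the intervention arm (Blinding), that is 28 x 20 = 560 counts, none with a described check.

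**4. Illustration of size.** Let t be true completion and o the share of missed sessions reported as done. Both are assumed; neither is in the documents. Then

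reported completion = t + (1 - t) x o.

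Scheduled first listens: 20 x 7 = 140. At t = 70%, 98 are done and 42 missed.

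- o = 10%: (98 + 4.2)/140 = 73%
- o = 30%: (98 + 12.6)/140 = 79%
- o = 50%: (98 + 21)/140 = 85%

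Applied to people rather than sessions, t = 60% with o = 10%, 20%, 30% and 50% gives 64%, 68%, 72% and 80%. At t = 80%, o from 0% to 50% gives 80% to 90%.

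**5. Direction.** The formula allows only over-reporting. Forgotten plays work the other way. At t = 70% and o = 30%, the 12.6 sessions added would be cancelled if 12.6/98 = 12.9% of completed sessions went unreported. The documents cannot say which effect is larger.

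**6. Comparison with sampling error.** Exact (Clopper-Pearson) 95% intervals with n = 20 are 36% to 81% for 12/20 and 56% to 94% for 16/20. The shifts in step 4, taken per person, fall inside these intervals.

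**The case against.** The strongest reply has four parts.

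*The documents do not show that the figures will be too high.* This stands. A reader might infer that uptake and acceptability are bound to be overstated, or that the error runs in one direction only. The documents contain no evidence on size or direction, and step 5 shows how under-recall of replays could offset over-reporting. Upward is the more plausible direction given the setting, but no more than that.

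*Not everything passed through the researcher.* This also stands. A reader might infer that all the use and acceptability data came from conversation with the primary researcher. The overall feedback was written in the concluding measures, and the mode for the listening counts is not given, so a weekly online form cannot be excluded. The weakness in the counts does not depend on the mode, however: they are unverified self-report either way.

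*Any bias is lost in the noise at n = 20, and no decision rule turns on it.* This stands only in part. The illustrated shifts do lie within sampling uncertainty. But a confidence interval displays sampling error and not reporting error, and reporting error does not shrink with more participants. The missing feasibility criterion, and the naming of anxiety and depression as primary in Questionnaires for the outcome variables, are separate matters to reconcile. They do not make the use data sounder.

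*The website may not be able to log plays.* Its capability is not stated, so the remedy needs a fallback.

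**Conclusion.** The point holds in a limited form. The plan ties its feasibility outcome to self-reported listening and to weekly feedback given in identifiable contact with the primary researcher, and describes nothing against which either could be checked. Use and acceptability may be misreported, most plausibly upward.

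The documents give no basis for sizing this. The 3 to 15 point inflation illustrated at 70% true completion (73% to 85% reported) rests wholly on assumed values for true completion and over-reporting, and on no offsetting under-recall. That the counts were taken in the phone or email contact is a reasonable inference, not a documented fact. The end-of-trial feedback is outside the criticism of the weekly contact.

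This is a weakness in measurement worth correcting, because a better method is cheap. It is not evidence that the pilot's figures are wrong.

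**What to change.** 1. Give each intervention participant an individual access link to the study website, log plays per recording per week, and report logged plays alongside self-reported counts as the adherence data. Disagreement between the two is itself a useful feasibility finding.
2. Put the weekly listening and feedback questions on the online survey platform already used for the other measures, under a study code, for every intervention participant. This gives one mode for all.
3. Keep the weekly phone or email contact as planned. Reducing it would change what participants receive.
4. Leave the concluding feedback in its present mode.
5. If no logs can be obtained, report adherence as unverified self-report, state the limitation, and do not carry the figure unadjusted into main-trial planning.

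**Cost.** Minor website set-up, one short weekly form, and a consent sentence on usage logging. Logs miss offline replays and do not prove attentive listening, which is why they should stand beside self-report and not replace it.

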The results of the questionnaires in the online SurveyMonkey⁴⁰ format were converted to an SPSS data file. SPSS⁴³ was used to provide baseline descriptive statistics for the control and intervention groups. Independent sample t-tests were then conducted in order to establish participant results for the outcomes of interest pre and post intervention. The comparison of group differences over time was undertaken using linear mixed effects modelling with group, time and group time interaction. Group time interaction was included in the

model as the formal test for the efficacy of the intervention. Linear mixed effects modelling was conducted using Stata statistical software.⁴⁴ A second model including suggestibility was then undertaken. Results were considered statistically significant at $p < 0.05$.

Sample size justification

Power calculations for the study were carefully considered. Current recommendations for pilot RCT sample sizes vary significantly, as they are by definition investigative in nature and the standardized effect size is unknown. For a main trial planned with 90% power and two-sided 5% significance in mind, Whitehead et al.⁴⁵ recommend a minimum of 10 participants per study arm in the pilot trial.

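### Optional gain: report a baseline-adjusted week-7 difference with 95% CI beside the group-by-time test, and clarify or drop the pre and post t-tests

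*Combined protocol and SAP*

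**What the plan says.** The Statistical analyses section plans three things after baseline descriptive statistics by group.

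- T-tests: "Independent sample t-tests were then conducted in order to establish participant results for the outcomes of interest pre and post intervention".
- A longitudinal model for group differences: "linear mixed effects modelling with group, time and group time interaction". The interaction is included in the "model as the formal test for the efficacy of the intervention".
- A second model that adds suggestibility.

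The threshold is common to all of them: "Results were considered statistically significant at" p < 0.05. No confidence interval is mentioned. The outcome's own baseline value is not a covariate in any stated model, and nothing says that the arms share a baseline mean.

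The data for a baseline adjustment exist. Under Procedure, after week seven, "participants completed the outcome scales assessed at the beginning of the study", and the control group completed the closing measures at the same time. Under Blinding, 20 participants were allocated to each arm.

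On the status of these outcomes, the Outcome measures section says both "The primary outcome was to establish the feasibility of the trial" and "Our primary outcomes of interest were anxiety and depression".

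**The concern.** Two things attract attention.

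**The t-test sentence is unclear.** An independent-sample test of outcomes before and after treatment can be read in three ways.
- Arm against arm at each visit, the more natural reading: the baseline tests examine differences that randomization makes due to chance, and the week-7 tests ignore baseline.
- Before against after within an arm: an independent-sample test ignores the pairing.
- Arm against arm on change scores: with complete data this repeats the interaction test.

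**The baseline scores are not used to best effect.** The week-7 t-test gives baseline no weight. The interaction, with the arms free to differ at baseline, subtracts baseline in full, which fixes its slope at 1. A model that estimates the slope is usually more precise.

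What is at stake is the width of the between-arm interval in a 40-person pilot, and the clarity of its secondary p-values. A later trial would take its planning values from these estimates.

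**Working it through.** **Plan's own figure.** The only sample-size figure is a minimum of 10 per arm taken from a cited source. The section says that "the standardized effect size is unknown" and gives no SD or correlation, so the figure cannot be rebuilt. The check below does not depend on it.

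**Inputs.** From the document: n = 20 per arm, two visits, 0.05 threshold. Assumed: two-sided test, complete data, equal SD at both visits (set to 1), pre-post correlation ρ of 0.3 / 0.5 / 0.7, and a true effect of 0.8 SD for power.

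**Step 1: interaction and change score.** With two visits and complete data, the group-by-time estimate equals the between-arm difference in mean change. In a simulated check dataset both gave −2.4206 with SE 1.3285.

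**Step 2: variance of the arm difference, in units of 2·SD²/n.**
- Week-7 t-test: 1
- Group-by-time: 2(1 − ρ), giving 1.40 / 1.00 / 0.60
- Baseline-adjusted: (1 − ρ²)(1 + 1/(N − 4)) with N = 40, where the last factor (1.028) pays for the estimated slope. This gives 0.935 / 0.771 / 0.524.

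**Step 3: 95% CI half-width** = t × √(2V/20), with t = 2.024 on 38 df (2.026 on 37 df for the adjusted model). Example at ρ = 0.3: group-by-time 2.024 × √0.140 = 0.757; adjusted 2.026 × √0.0935 = 0.620. Power uses the noncentral t.

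| | ρ = 0.3 | ρ = 0.5 | ρ = 0.7 |
|---|---|---|---|
| Half-width, week-7 t-test (SD) | 0.640 | 0.640 | 0.640 |
| Half-width, group-by-time | 0.757 | 0.640 | 0.496 |
| Half-width, adjusted | 0.620 | 0.563 | 0.464 |
| Adjusted narrower than group-by-time | 18% | 12% | 6% |
| Adjusted narrower than week-7 t-test | 3% | 12% | 28% |
| Power at 0.8 SD: t-test / group-by-time / adjusted | 69 / 55 / 72% | 69 / 69 / 80% | 69 / 89 / 93% |

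Simulation agreed: at a true effect of 0.5 SD all three estimates were unbiased, and the adjusted test's type I error was 5%.

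**Step 4: equivalent size.** Solving t × √(2·2(1 − ρ)/n) = 0.620 / 0.563 / 0.464 for n gives 29.3 / 25.5 / 22.7. Group-by-time would therefore need about 30 / 26 / 23 per arm to match the adjusted model at 20.

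**Step 5: where the gain fails.**
- Against the week-7 t-test, the adjusted interval is 1.5% wider at ρ = 0, 1.0% wider at 0.1, 0.3% wider at 0.15 and 0.6% narrower at 0.2.
- Let the week-7 SD be k times the baseline SD. Group-by-time variance becomes k² + 1 − 2ρk, and adjusted variance k²(1 − ρ²) × 1.028. At ρ = 0.7, k = 1.2 these are 0.760 and 0.755, so the adjusted interval is 0.3% narrower. At ρ = 0.7, k = 1.25 they are 0.8125 and 0.819 (0.5% wider). At ρ = 0.8 the adjusted interval is 1.3% wider for k = 1.2 and 1.5% wider for k = 1.25. If the SD shrinks, the gain grows.

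**Step 6: baseline tests, arm-against-arm reading only.** Seven scores are measured at both visits (GAD-7, PHQ-9, pain VAS, two Brief-COPE subscales, PCS, PDI). The chance of at least one p < 0.05 at baseline is 1 − 0.95⁷ = 30% if the scores are independent. Simulation gave 18% at a between-score correlation of 0.7.

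**The case against.** The strongest reply is that the plan has already settled what matters. It names one formal efficacy test, and that test is valid. A reader might infer that a week-7 t-test disagreeing with the interaction leaves two rival efficacy verdicts. The text does not support that, because it ranks the interaction first and uses the t-tests only to describe results. This part of the reply stands.

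A reader might also infer that the plan commits to significance tests of baseline balance. It does not say so. It promises descriptive statistics at baseline, and baseline p-values follow from only one reading of the t-test sentence. The 18 to 30% figure is conditional on that reading. What stands is that the sentence is unclear.

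A third inference would be that adjustment always wins. Step 5 shows that it does not, although the losses found there are at most about 1.5%.

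The most practical objection concerns timing. The text describes completed work. Replacing the named efficacy test afterwards with a more powerful one, and presenting that as the sole result, would be a post hoc change. This stands, and it shapes the fix.

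Finally, feasibility is called the primary outcome, so precision on symptom scores matters less here. That lowers the priority but does not remove the point, since anxiety and depression are also called primary outcomes of interest. The second model with suggestibility is no answer either: it does not adjust for the outcome's own baseline value.

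**Conclusion.** The point holds as an optional, low-cost improvement in precision and reporting. It is not an error in the efficacy analysis: nothing in the document makes the group-by-time test biased or invalid.

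Under complete data and equal SDs, the adjusted interval is 6 to 18% narrower than group-by-time over correlations of 0.7 down to 0.3. Power at 0.8 SD rises by 4 to 17 percentage points (89 to 93%, and 55 to 72%). Over the week-7 t-test the power gain runs from 3 points at correlation 0.3 to 24 at 0.7. These sizes rest on correlations, an SD ratio and an effect size that the document does not give, so they are a range and not an estimate for this trial. Two findings do not depend on them: no between-arm estimate with a confidence interval is promised, and the t-test sentence needs rewording on any reading.

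**What to change.** - For each of the seven scores, report the between-arm week-7 difference with a 95% CI from a baseline-adjusted model. Either enter the baseline score as a covariate, or fit the mixed model with the arms constrained equal at baseline. The second form keeps participants who have no week-7 score. In the check dataset the two gave similar answers (−2.569, SE 1.076, and −2.561, SE 1.116).
- Keep the group-by-time result and show the adjusted estimate beside it. Label the adjusted analysis as added after the original plan, and do not present it as the only efficacy p-value.
- Summarise baseline by arm with means and SDs, without p-values.
- Drop the t-tests, or replace them with descriptive estimates with 95% CIs, paired if they are within arm. State which comparison is meant.
- Report the observed pre-post correlation and the SD at each visit, so that a later trial can see which method is more precise.

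Cost: one residual degree of freedom, about 2.8% of variance for the estimated slope (already counted above), a changed model line, and the post hoc label. No new data, visits or participants are needed.
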